Study Design	
Study design: Pilot randomized, single site clinical trial with blinded analysis
 
Participant recruitment and study site: We will recruit participants interested in using the ENG contraceptive implant but not currently at risk for pregnancy from University of Utah Hospital and Community clinics, and through targeted social media ads. All study procedures will occur at the University of Utah Hospital Outpatient OBGYN Clinic
 
Sample size: This is a pilot proposal to recruit a total of 40 participants across 2 study arms: (1) ENG implant only (n=20) and (2) UPA + same day ENG implant insertion (n=20). Our null hypotheses are:
 
 
1) ENG implant along with UPA administration in the presence of a dominant ovarian follicle will not change the expected 97% ovulation suppression within 5 days of UPA use.
 
2) ENG implant insertion alone in the presence of a dominant ovarian follicle will not sufficiently interrupt ovulation.
 
 
Inclusion criteria: Healthy people, age 18-35 years, fluent in English and/or Spanish, BMI < 30 kg/m^2, no known contraindication to either the ENG contraceptive implant or UPA using the CDC Medical Eligibility Criteria for Contraceptive Use 2016, not currently pregnant and not at risk of pregnancy (defined as not having penile-vaginal intercourse or using a non-hormonal method of contraception such as a barrier method, condoms, diaphragm, or cervical cap, a copper IUD, or permanent contraception), know the date of their last menstrual period, have a regular menstrual cycle (24-35 days), be willing to comply with the study requirements, and be willing to avoid pregnancy for study duration.
 
Exclusion criteria: Current pregnancy or breastfeeding, use of hormonal contraception or exogenous hormones (estrogen, progestogen, or HCG) in the last month (or past 6 months for depo medroxyprogesterone acetate) planned use during the study, vaginal bleeding of unknown etiology, allergy to UPA or ENG, regular or planned use of glucocorticoids during the study, or current or planned use of any medication that potentially interacts with UPA or ENG.
 
Participant adherence: Screening protocol will ensure willingness to comply with all study procedures. Participants will receive compensation for each component of the protocol.

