Study Flowchart	<pre> graph TD     A[Phone Screening for Eligibility] --> B[Screening Visit 1- history, exam, TVUS]     B --> C[Screening Visit 2- Day 20-24 progesterone]     C --> D[Screening Visit 3-7 (+/-2)- Start TVUS 3X/week on day 7, then daily when follicle ≥ 13mm]     D --> E[Treatment Visit 1 (Follicle ≥ 14mm) – Randomization TVUS, serum LH, P4 and E2]     E --> F[Group 1- ENG Implant]     E --> G[Group 2- oral UPA + ENG Implant]     F --> H[Treatment Visit 2-8 (days 2,3,4,5,6,7,8)- TVUS, serum LH, P4 and E2]     G --> H     H --> I[Exit Visit (Treatment Day 14)- TVUS, serum LH, P4 and E2]   </pre>

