
	
transvaginal ultrasounds until either follicle rupture is documented, the follicle is <12 mm on two consecutive visits, or Day 8 ultrasound occurs (7 days after implant insertion), whichever occurs first.
 
Treatment Day #14 (Exit Visit): Repeat ultrasound will occur on Day 14 following ENG implant insertion, and this will be the exit visit.
 
Data collection: Source documents for each participant and visit number will be completed by the study personnel at the time of the visit. Form development, data collection, and data management will occur in RedCAP, secure web platform for building and managing online databases and surveys. Source documents maintained in individual participant binders.
 
Assessing and reporting adverse events: The reporting period for AEs is the period immediately following the subject signing the informed consent through the 30 days following the final study visit. Each visit will include assessment of how the participant felt since the last visit, review of adverse event reports, implant insertion site reactions, lab results, and vital signs and physical exam findings. AEs will not be reported for screen failures unless a SAE is experienced during screening. For all AEs, the investigator will pursue and obtain information adequate to determine the outcome of the AE and to assess whether it met criteria for a SAE. Participants who have ongoing AEs or SAEs will be followed until resolution or stabilization or referred for additional care. AEs will be documented both on source documents and in the clinical database with SAEs reported per IRB guidelines. Participants will be provided instructions for contacting the study site to report any untoward medical occurrences. With permission from the participant, whenever possible records from all non-study medical providers related to medical occurrences will be obtained for review. AEs and SAEs will be reviewed by the Data Safety Monitoring Board as below (section 2.9).

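### Adverse events are reportable for 30 days after the exit visit, but no contact is scheduled in those days and no itemised visit lists a pregnancy test

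*Combined protocol and SAP*

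**What the plan says.** Study Procedures, Assessing and reporting adverse events, sets the window, which opens at consent and runs "through the 30 days following the final study visit". The final visit is fixed under Treatment Day #14 (Exit Visit): "Repeat ultrasound will occur on Day 14 following ENG implant insertion, and this will be the exit visit".

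The same adverse-event paragraph says how events are found. Active inquiry belongs to visits: "Each visit will include assessment of how the participant felt since the last visit, review of adverse event reports". For everything else the text gives one route: "Participants will be provided instructions for contacting the study site to report any untoward medical occurrences". It also promises that adverse events still open will be followed or referred, and that outside medical records will be sought, with permission, for occurrences that come to light.

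The Study Flowchart lists the content of the last visit as "Exit Visit (Treatment Day 14)- TVUS, serum LH, P4 and E2". The earlier visits in the flowchart and under Participant procedures consist of history, examination, transvaginal ultrasound, progesterone, LH and estradiol. Current pregnancy is an exclusion, but no test is named to establish it.

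On pregnancy risk, the inclusion criteria treat as not at risk those who do not have penile-vaginal intercourse, and also a person "using a non-hormonal method of contraception such as a barrier method, condoms, diaphragm, or cervical cap". Copper IUD users and those with permanent contraception qualify too.

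**The concern.** The plan declares a 30-day reporting period after exit but schedules nothing in it. An event that begins or is first noticed in that period enters the database only if the participant takes the initiative. What is not asked then cannot be recovered at analysis.

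Pregnancy is the event most exposed to this gap. Treatment is given when a lead follicle of at least 14 mm is present, and whether that follicle ruptures afterwards is what the trial measures. Some participants may be relying on a barrier method. If one of them ovulates and conceives in the treatment cycle, the pregnancy may not be apparent at Day 14, and she leaves the study with a new implant in place (after UPA as well, in one arm).

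At stake is the meaning of a zero. If the final report shows no late adverse events and no pregnancies, a reader could not tell whether none occurred or nobody asked.

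**Working it through.** The documents state no figure for this point, so there is nothing to reproduce. The check is a read-through of the schedule followed by day counts.

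**1. Scheduled contact after exit.** Visits run from screening through Treatment Days 1 to 8 to the Day 14 exit. No call, message, survey or visit is listed later. Data collection describes source documents by participant and visit number, so no form is described for the period after exit.

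**2. Length of the uncovered period.** The day count is ambiguous. Study Procedures equates Day 8 with seven days from insertion, which makes Treatment Day 14 thirteen days from insertion. The exit-visit text can also be read as fourteen days from insertion.
- Exit at 13 days: window closes at 13 + 30 = 43 days; 30/43 = 69.8%.
- Exit at 14 days: window closes at 14 + 30 = 44 days; 30/44 = 68.2%.

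These are shares of the post-treatment period only. The declared window opens at consent, and the documents do not fix how long screening takes. If screening is assumed to last 3 to 5 weeks, the share of the whole window (using 44 days) is 30/(44 + 21) = 30/65 = 46% down to 30/(44 + 35) = 30/79 = 38%.

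**3. Time from rupture to exit.** Day 2 is one day after insertion and Day 8 is seven.
- Exit at 13 days: 13 − 1 = 12 days down to 13 − 7 = 6 days.
- Exit at 14 days: 14 − 1 = 13 days down to 14 − 7 = 7 days.

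A rupture seen during daily monitoring is thus 6 to 13 days old at exit, and a later one is younger. Null hypothesis 1 says that the implant with UPA "will not change the expected 97% ovulation suppression within 5 days of UPA use". That figure covers only the first 5 days. A rupture postponed beyond them falls at most 13 − 5 = 8 or 14 − 5 = 9 days before exit. At 30 days after exit, a Day 2 to 8 rupture is 6 + 30 = 36 to 13 + 30 = 43 days old. The existing window is therefore long enough; it lacks only a contact.

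**4. What active contact would buy.** If *m* participants are asked and none reports an event, the one-sided 95% upper bound on the event risk is 1 − 0.05^(1/*m*).
- *m* = 40: 1 − 0.05^(1/40) = 7.2%.
- *m* = 20 (one arm): 1 − 0.05^(1/20) = 13.9%.

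These bounds are wide, as expected in a pilot, but they can be stated. Without active contact *m* is unknown and no bound follows from a zero.

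**The case against.** The strongest reply is that the scheme is coherent as it stands. A reporting period is not a promise of active follow-up. Inquiry at visits, instructions for contacting the site, retrieval of outside records and follow-up of open events together make an ordinary passive system. The Statistical Analysis Plan names no safety or pregnancy endpoint, and the primary outcome does not depend on any of this. That stands as far as it goes: there is no contradiction in the text. It does not answer the point that late events left unasked about are lost.

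The second reply is that the text is incomplete. The opening pages were removed, and section 2.9, on the Data Safety Monitoring Board, is cited but not supplied. A pregnancy test or a follow-up call could be described there. This stands and limits the conclusion to the supplied text.

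Several stronger readings are tempting and are not supported:
- *All adverse events depend on self-report.* They do not. Events up to exit are asked about at each visit, and open ones are followed.
- *The protocol expects ovulation on the implant alone.* Null hypothesis 2 is a hypothesis to be tested, and the Power/Sample Size text says that data on mid-cycle insertion are lacking.
- *A probability of at least one pregnancy can be given.* The documents contain no barrier failure rate and no count of barrier users. All 40 participants receive an implant and 20 also receive UPA, with unknown effect on that risk.
- *A Day 14 pregnancy test would miss particular rupture days.* The exit day is ambiguous by one day, and the documents say nothing on test performance.

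**Conclusion.** The point holds for events that start or become apparent after exit. For the last 30 of about 43 to 44 post-treatment days, the supplied text relies on the participant to contact the site. No itemised visit lists a pregnancy test, although barrier users are eligible, and a treatment-cycle pregnancy may not be apparent by exit. That last step rests on the 6 to 13 days between a monitored rupture and exit and on general clinical reasoning, not on a statement in the documents.

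This is a gap in safety ascertainment. It leaves the primary outcome, delay of follicle rupture by 5 days, and its analysis untouched. It is best classed as a cheap improvement, and it falls away if section 2.9 or the removed pages already provide the contact.

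A reader might infer that the reporting period should instead be cut back to Day 14 so that the wording matches the visits. That would discard serious events that participants report unprompted in the following 30 days, leaving less safety information than the plan collects now.

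**What to change.** Add one automated REDCap survey to every treated participant at 30 days after the exit visit. It should ask about new adverse events, implant-site problems and pregnancy status. Optionally, hand out a home urine pregnancy test at exit and record its result in the survey. In the report, give by arm the number who responded beside the number of events, so that a zero has a denominator.

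The survey does not address how current pregnancy is ruled out at entry. If section 2.9 or the removed pages do not say, one sentence in Study Procedures should.

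The cost is a short amendment and one survey form in a system already in use, plus up to 40 home tests if that option is taken. No clinic visit or new staff is needed, though chasing non-responders takes some coordinator time. The downside is some non-response and slightly later study completion.

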Study Procedures	
Randomization scheme: block randomization with block size of 4
 
Blinding protocol: This study will not be blinded as a pilot. The feasibility of the study, including clinic space limitations and provider time, relies on the same healthcare provider for implant insertion and ultrasound in many patients. All statistical analyses will be blinded to the statistician.
 
Participant procedures:
 
Screening Visit (Screening Visit 1): Subjects will be screened for eligibility and interest in the study. Each subject will have the study explained and, if they desire to participate, she will sign the informed consent prior to any study procedures. The screening visit will include: review of medical, surgical and social history, medications, menstrual dating, sexual history and contraceptive use, physical exam, including breast and pelvic, and a transvaginal ultrasound to ensure ability to document ovarian follicular activity in the treatment cycle.
 
Progesterone Visit (Screening Visit 2): This brief visit will occur on days 20-24 of the menstrual cycle and may be combined with the screening visit (Visit 1) if the timeframe is met. This visit will include a review of any interim changes (if completed separate from the screening visit) in history, medications, pregnancy risk/contraception, and a serum progesterone level will be drawn. The participants will notify the study coordinator of the 1st day of their next menses.
 
Ovarian monitoring (Screening Visits 3-7 +/- 2 visits): Participants will undergo transvaginal ultrasound evaluation of their ovaries three times a week starting on cycle day #7 (+/- 2 days). If/ When we identify a lead follicle with a mean diameter of >13mm in at least 2 dimensions, we will switch to daily monitoring.
 
Treatment Day #1 (Treatment Visit #1): Once a lead follicle (<math>\geq 14mm</math>) is identified then participants will be randomized to one of two treatment groups:
 
 
1) ENG implant insertion
 
2) UPA 30mg PO tablet and same-day ENG implant insertion
 
 
Assigned treatment will be administered (UPA and/or ENG implant insertion). We will obtain serum progesterone, LH levels, and estradiol levels.
 
Treatment Days #2-8 (Treatment Visits #2-8): Participants will follow up daily for Days 2-8. Each day we will obtain transvaginal ultrasound measurement of ovarian follicle size, serum progesterone, LH levels, and estradiol levels. We will obtain daily

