
Statistical Analysis Plan
	
The investigator and study team will be responsible for analyzing the study data. The official clinical database in RedCAP will not be analyzed until medical/scientific review has been completed, protocol violators have been identified (if appropriate), and data has been declared complete.
 
Variables/Time Points of Interest
 
The primary outcome is delay in rupture of the dominant follicle by 5 days (yes/no) between group 1 (ENG implant alone) and group 2 (UPA with same day ENG implant). If the date of follicle rupture was unclear by ultrasound alone, we will utilize serum hormone levels to adjudicate day of rupture. These measures include day of follicle collapse, day and value of highest LH, day and value of highest progesterone level. We will use an estradiol level of >100pg/ml to confirm the enlarged follicle is the dominant follicle on the treatment day.
 
Statistical Methods
 
The primary and secondary dichotomous outcome measures of ovulation by 5 days will be assessed by Wilcoxon sign rank test and demographic will be analyzed using descriptive statistics.
 
Power/Sample Size:
 
This is a pilot study to obtain point estimates for future study proposals. Current data on ovulatory function with mid-cycle implant insertion or the pharmacodynamics interactions between same day UPA and ENG are lacking.

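### The fallback that dates rupture from hormones when scans are unclear has no masking to arm, no named cut day and no order of evidence, so a case spanning the 5-day cut can be scored either way

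*Combined protocol and SAP*

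**What the plan says.** In the Combined protocol and SAP, the Statistical Analysis Plan (Variables/Time Points of Interest) defines the endpoint: "The primary outcome is delay in rupture of the dominant follicle by 5 days (yes/no"), compared between the implant-alone and UPA-plus-implant groups. Ultrasound comes first, and hormones are the fallback: "If the date of follicle rupture was unclear by ultrasound alone, we will utilize serum hormone levels to adjudicate day of rupture". The evidence is listed without ranking: "These measures include day of follicle collapse, day and value of highest LH, day and value of highest progesterone level". The same section opens with "The investigator and study team will be responsible for analyzing the study data".

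On masking, Study Procedures (Blinding protocol) says "This study will not be blinded as a pilot" and then "All statistical analyses will be blinded to the statistician". It adds that one provider will often both insert the implant and scan.

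On timing, Study Procedures (Treatment Days 2-8) says "Each day we will obtain transvaginal ultrasound measurement of ovarian follicle size, serum progesterone, LH levels, and estradiol levels". Daily scans end at documented rupture, or when the follicle is below "12 mm on two consecutive visits, or Day 8 ultrasound occurs (7 days after implant insertion), whichever occurs first". The Study Flowchart adds one further scan and hormone sample at the Treatment Day 14 exit visit.

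**The concern.** The hormone fallback sets the value of the primary endpoint before any analysis starts. Masking the statistician at the analysis stage does not protect a value that unmasked staff have already assigned. The plan gives the task to the study team and does not say that the arm is withheld.

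Three further gaps leave room for judgement at this step:

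- The 5-day cut is not tied to a Treatment Day.
- No threshold, offset or order of precedence applies when LH and progesterone point to different days.
- No rule scores a participant whose daily scans stopped for a small follicle before the cut without documented rupture.

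The pilot's stated purpose is to supply point estimates for later studies, so a wrongly scored case would carry forward into their planning.

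**Working it through.** **Conventions.** Rupture day is the first scan day showing collapse. With cut Day c, a follicle collapsed by the Day c scan is not delayed. The documents do not state this convention; it is assumed here.

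**1. Which day is the cut?** Study Procedures equates Day 8 with 7 days after insertion, so days after insertion = Treatment Day − 1 (8 − 1 = 7, as stated). Five days after insertion is then Treatment Day 5 + 1 = 6. Reading the 5 as a day label gives Day 5. The numbering is not fully consistent: the exit visit is described as Day 14 following insertion, while the Day 8 count makes Treatment Day 14 only 14 − 1 = 13 days after it. Both cuts are carried below.

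**2. When can scans leave status at the cut open?** Let a be the last intact scan and b the first collapsed scan, within Days 1-8. The pair spans the cut if a < c < b.

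| Missed or unreadable scans | Patterns | Spanning, c = 5 | Spanning, c = 6 |
|---|---|---|---|
| None | 7 | 0 | 0 |
| One | 6 | 1 (4,6) | 1 (5,7) |
| Two consecutive | 5 | 2 (3,6; 4,7) | 2 (4,7; 5,8) |

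These are pattern counts, not probabilities.

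**3. The small-follicle stop.** The follicle is at least 14 mm on Day 1, so two consecutive readings below 12 mm can be complete on Days 3 to 8, which is 6 possible stop days. The stop precedes a Day 5 cut on Days 3-4 (2 of 6) and a Day 6 cut on Days 3-5 (3 of 6). It ends daily ultrasound only; daily serum is still planned through Day 8. What is missing is the scoring rule.

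**4. Size.** One case out of 20 is 1/20 = 5 percentage points in its arm. With m1 and m2 unresolved cases in the two arms, the risk difference can range over (m1 + m2)/20, which is 5m points for m = m1 + m2 (m = 1, 2, 3 gives 5, 10, 15). Scoring all cases the same way in both arms shifts the difference by only |m2 − m1|/20. With one case per arm, that shift is 0, against a full range of 10 points. For scale, the exact 95% interval for 19/20 is 75.1% to 99.9%.

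**5. Day of highest progesterone.** Without any assumption: no serum is scheduled between Day 8 and Day 14, so a peak after Day 8 can register only on those two samples. Going further needs a rupture-to-peak lag, which the documents do not give. As an illustration, take lags of 5-9 days and the nearest sample as the highest:

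- Over rupture Days 2-8 (7 × 5 = 35 combinations), the highest sample is Day 8 or Day 14 in 34; the exception is Day 2 + 5 = Day 7.
- For rupture on Day 5 v Day 6, both register on Day 14 at 3 of 5 lags. For Day 6 v Day 7, it is 4 of 5.
- With ties split, the share registering on Day 14 is 0.7, 0.9 and 1.0 for rupture on Days 5, 6 and 7. The best rule is right in ½(1 + 0.2) = 60% (Day 5 v 6) and ½(1 + 0.1) = 55% (Day 6 v 7), where 50% is chance.

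A simulation with noise and ruptures spread evenly over Days 4-8 (guessing is right 60% of the time) gave the following best accuracy:

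| Assumed mean lag | Day 5 cut | Day 6 cut |
|---|---|---|
| 7-8 days | 64-73% | 60% |
| 6 days | 81-83% | 63-69% |
| 5 days | 82-87% | 73-82% |

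**6. Does replacing peak day matter once LH is used?** For one-day straddles, assume independent lags and a first progesterone rise 0-2 days after rupture (67% alone).

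- LH peak 1-2 days before rupture settles half the cases. With peak-progesterone day: 0.5 + 0.5 × 0.60 = 80%, or 0.5 + 0.5 × 0.55 = 77.5%. With first rise: 0.5 + 0.5 × 0.667 = 83%.
- LH peak 0-2 days before rupture settles a third. With peak day: 1/3 + 2/3 × 0.60 = 73%, or 1/3 + 2/3 × 0.55 = 70%. With first rise: 1/3 + 2/3 × 0.667 = 78%.

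The gain is about 3 to 8 points. Most of the accuracy comes from LH, which the plan already lists.

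**The case against.** The design line describes the analysis as blinded, the Blinding protocol gives a feasibility reason for unblinded care, and the dating sits inside the SAP. One can argue that the dating is meant to be masked and that the text is merely unclear. That much is fair: masking of this step is unstated rather than shown to be absent. But the masking sentence covers statistical analyses, while the adjudication is given to the study team. Masking it needs no clinic space or provider time, so the feasibility reason does not reach it.

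The cut can be derived as Day 6 from the document's own count. That stands, and one line would settle it.

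A reader might infer that stopping scans early leaves no information at the cut. The documents do not support that, because daily serum continues to Day 8 and a Day 14 scan follows.

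A reader might also infer that day of highest progesterone is a poor dater whatever the circumstances, or that replacing it would greatly improve accuracy. Neither follows. The first depends on a lag that is not in the documents, with moderate separation at short lags. The second gains only a few points once LH is used, again under assumed lags.

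Finally, this is a 40-person pilot with no power claim, and one case is small against sampling error. That limits the weight of the point but does not remove it, since the remedy is cheap.

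**Conclusion.** The point holds as a gap in how the primary endpoint is assigned. Followed as written, the plan lets someone who knows the arm decide a case whose possible rupture days span the cut, with no fixed cut day and no order of evidence. The size is up to 5 percentage points in an arm per case and 5m points in the risk difference for m cases, assuming 20 analysed per arm.

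A reader might infer that the result will be biased, or biased towards one arm. The documents do not support that: the number of unclear cases and the direction of any error are unknown, and with complete, readable scans no intact-to-collapsed pattern spans the cut. Cases whose possible days all fall on one side are unaffected.

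The masking, cut-day, ordering and small-follicle gaps rest on the text alone. The progesterone-peak point is secondary: the sampling gap between Day 8 and Day 14 is a fact of the schedule, but its effect on dating is conditional on assumed lags. The change should be made; confidence is medium.

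**What to change.** In the Statistical Analysis Plan, Variables/Time Points of Interest:

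1. State the cut as a Treatment Day (Day 6 by the document's own count).
2. Limit adjudication to cases whose last intact and first collapsed scans span the cut, or whose small-follicle stop leaves status at the cut undetermined. All others keep the observed status.
3. Fix the order of evidence in advance: LH-peak day first, then the daily Day 1-8 progesterone series against a threshold the sponsor sets. Do not let day of highest progesterone decide a case when it falls on Day 8 or Day 14.
4. Have the already-blinded statistician apply the rule to an extract without the arm, before allocation is merged.
5. Report the number adjudicated per arm. Add a sensitivity analysis that scores cut-spanning cases in opposite directions by arm (all delayed in one and not delayed in the other, then reversed), as well as the same way in both arms. Only the opposite scoring bounds the full 5m-point range.

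The cost is SAP wording and a short program run on serum already planned; there is no extra visit, assay or reader. The sponsor must commit to the rule now. Some cases will stay uncertain, and treatment could shift hormone timing differently by arm. Unblinded scanning can still influence which cases become unclear, and should be stated as a limitation.

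### The only test named for the primary outcome, the Wilcoxon signed-rank test, does not fit a yes/no outcome compared between two independent arms, and no between-arm estimate or interval is specified

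*Combined protocol and SAP*

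**What the plan says.** In the Statistical Analysis Plan, Variables/Time Points of Interest defines the primary outcome as "delay in rupture of the dominant follicle by 5 days (yes/no) between group 1 (ENG implant alone) and group 2", the second group being UPA with same-day implant. Statistical Methods then gives the analysis: "The primary and secondary dichotomous outcome measures of ovulation by 5 days will be assessed by Wilcoxon sign rank test". The rest of that sentence covers only descriptive statistics for demographics, so this is the sole inferential method in the plan.

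The design is parallel-group. Study Design (Sample size) plans to "recruit a total of 40 participants across 2 study arms", 20 in each. Study Procedures states that "participants will be randomized to one of two treatment groups", using "block randomization with block size of 4". No matched pairs, crossover or within-person comparison is described for this outcome.

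On purpose, Power/Sample Size says: "This is a pilot study to obtain point estimates for future study proposals". No risk difference, ratio, confidence interval, alpha or power is stated. The only numerical rate is in the first null hypothesis, that implant plus UPA "will not change the expected 97% ovulation suppression within 5 days of UPA use". No rate is given for the implant alone.

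**The concern.** The signed-rank test works on differences, either within pairs or between single observations and a fixed value. Two independent groups supply neither. To use it for the stated contrast, someone must decide which participant in one arm is set against which participant in the other. Randomising in blocks of 4 balances the arm sizes; it does not create pairs. If the arms end unequal, the participants left over are discarded.

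Two things are at stake. First, where the table is borderline, two analysts with the same data and equally outcome-blind pairings can fall on opposite sides of 0.05. Second, the pilot's product is a set of estimates for planning a later trial, and the named test yields neither a risk difference nor an interval.

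**Working it through.** **Inputs.** From the documents: 20 per arm, a binary outcome, and 97% suppression with UPA. Assumed: two-sided 0.05, every example count, and all implant-alone rates. The plan's own figure, 20 + 20 = 40, adds up but cannot be derived, since no alpha, power or implant-alone rate is given.

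**1. What the test becomes on paired 0/1 data.** Each difference is −1, 0 or +1. Zeros are dropped and the rest tie in size. Suppose the arms have x and y successes and k pairs are successes on both sides. The discordant counts are then b = x − k and c = y − k.
- Exact p = 2 × P(Binomial(b + c, 0.5) ≥ max(b, c)), which is the sign test or exact McNemar test.
- Normal approximation: z = |b − c| / √(b + c).

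Nothing in the data fixes k; the pairing does. It can run from max(0, x + y − 20) to min(x, y). Under random pairing it is hypergeometric.

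**2. One table in full: 16/20 v 10/20.** Here k runs from 6 to 10.
- k = 6: b:c = 10:4. Exact p = 0.180; z = 6/√14 = 1.60, p = 0.109.
- k = 10: b:c = 6:0. Exact p = 2 × 0.5⁶ = 0.031; z = 6/√6 = 2.45, p = 0.014.

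**3. Several tables.**

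| Table | Fisher p | Exact p over pairings | Share of pairings with p < 0.05, exact / normal |
|---|---|---|---|
| 16 v 10 | 0.096 | 0.031 to 0.180 | 4.3% / 29.1% |
| 19 v 13 | 0.044 | 0.031 or 0.070 | 35% / 100% |
| 19 v 12 | 0.020 | 0.016 or 0.039 | 100% / 100% |

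If one arm is 20/20, k can take only one value, so every pairing gives the same p.

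**4. How often it matters.** Summing over binomial outcomes with UPA at 97%:

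| Implant-alone rate (assumed) | P(call can depend on pairing), exact / normal | Power: Fisher / exact paired / normal paired |
|---|---|---|
| 60% | 9.6% / 12.6% | 81% / 73% / 87% |
| 70% | 7.5% / 17.9% | 56% / 43% / 68% |

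Over implant-alone rates from 40% to 90%, the chance of a pairing-dependent call is 0.1% to 9.6% (exact) or 1.3% to 17.9% (normal). With equal rates in both arms, type I error under random pairing peaks at 2.3% (exact) and 4.9% (normal).

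**5. The one-sample reading.** Both null hypotheses are worded within one arm, so a test against 0.97 might have been meant. With 19/20, the differences are nineteen of +0.03 and one of −0.97. The nineteen share rank 10 and the single one takes rank 20, so W+ = 190, W− = 20 and exact p = 0.0004. The exact binomial test of 19/20 against 97% gives p = 0.46. The test ranks the sizes of the differences and does not test the proportion, so it rejects on data that fit 97%. It also makes no comparison between arms.

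**6. What the pilot could report instead.** Risk difference with Newcombe 95% CI:
- 19/20 v 12/20: 0.35 (0.09 to 0.57)
- 19/20 v 13/20: 0.30 (0.05 to 0.52)
- 16/20 v 10/20: 0.30 (0.005 to 0.53)

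**The case against.** The best defence is that the wording is a slip for the Wilcoxon rank-sum test. That test takes independent groups and on 0/1 data is close to a chi-square test; without continuity correction it gives p = 0.0495 for 16 v 10 and 0.009 for 19 v 12. A statistician facing two unpaired columns would probably not invent pairs. This may well be so, but it is inference: the text names a different test, and a rank-sum test would still leave the risk difference and interval unspecified.

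A second point concerns size. The 9.6% and 12.6% count every table in which some pairing changes the call, even where few pairings do. If s is the share of pairings below 0.05, two analysts who pair at random and independently disagree with probability 2s(1 − s). Averaged over tables at 97% v 60%, that is 3.8% (exact) and 4.3% (normal). On a 10-point grid of implant-alone rates from 40% to 90%, the highest values are 3.8% and 6.2%. These figures stand as a separate and smaller measure of the same problem.

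Third, this is a pilot with no alpha or decision rule. No data are lost, the 2×2 table remains fully analysable, and an arm proportion needs no special method. That is right, and it limits the harm. It also makes the missing contrast and interval matter more than the p-value.

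**Conclusion.** The concern holds and should be corrected before analysis. The primary analysis cannot be carried out as written on the stated contrast, and nothing elsewhere in the documents supplies the missing pairing rule. The effect on a significance call is confined to borderline tables. The power loss applies to the exact version; the normal version has more power than Fisher's test at 97% v 60%. These sizes rest on an assumed 0.05 threshold, assumed implant-alone rates and random pairing. The mismatch between test and design, and the absence of a between-arm estimate with an interval, rest on none of those assumptions.

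**What to change.** In Statistical Methods, replace the signed-rank test with an unpaired test for two independent proportions, for example Fisher's exact test; another valid unpaired method such as Barnard's would also do. State that the main results are each arm's proportion with an exact or Wilson 95% CI, and the risk difference with a 95% CI, for example Newcombe's.

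If a Wilcoxon test was intended, name the rank-sum test. It is better suited to day of rupture than to the yes/no outcome, but that use would need a stated rule for participants with no observed rupture. This part is optional and the main correction does not depend on it.

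The cost is SAP wording only: no extra participants, visits or data.
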